#### 5.4 Statistical Analysis Software

5.4.1 Data manipulation, tabulation of descriptive statistics, calculation of inferential statistics, and graphical representations will be performed using SAS® version 9.3 or higher for Windows. If the use of other software is warranted, the final statistical methodology report will detail what software was used for what purposes.

#### 5.4.2 Data Management

- 5.4.2.1 The EDC system that will be used in the study is TrialMaster® (OmniComm Systems, Inc., Fort Lauderdale, FL, USA). It is a web-based software solution that allows clinical trial Sponsors and investigative sites to easily and securely collect, validate, transmit and analyze clinical study data. The system will be developed using OmniComm TrialMaster® EDC platform version: 4.2.1.23. OmniComm TrialMaster® EDC platform is compliant with the Food and Drug Administration (FDA) 21 CFR Part 11 regulations - electronic records; electronic signatures (last revised 01-Apr-2014)
- 5.4.2.2 Cardiac data should be transferred to eRT (eResearch Technology, Inc., Philadelphia, PA) the same day the data are obtained, if possible. Central Laboratory samples should be shipped to Clinical Reference Laboratory (Kansas, USA) on a daily basis, if possible, unless specific holiday or weekend schedules are in effect .
- 5.4.2.3 Data should be entered into the EDC (or paper CRF) within 5 business days of the study visit; queries should be appropriately addressed within 3 business days of receipt. During data cleaning and preparations for data lock, queries must be appropriately addressed by the site in a timely manner (2-3 business days).

MediStat Statistics in Medicine	DOCUMENT NUMBER: 029-BST-PLN-001	PAGE: 23 of 45
TITLE: Statistical Analysis Plan for study:  A Phase 2 Randomized, Double-Blind, Placebo-Controlled, Parallel-Cohort Study to Evaluate the Efficacy, Safety, Tolerability, and Pharmacokinetics of Once-Daily Application of Topical VDA-1102 Ointment for 28 Days in Subjects with Actinic Keratosis	EFFECTIVE DATE : 22/MAY/2017 REVISION NUMBER : 2.0	

### 5.4.3 Coding

- 5.4.3.1 Concomitant medications entered into the database will be coded using the WHO (World Health Organization) Drug Public Website Dictionary named WHOCC-ATC/DDD index, which employs the Anatomical Therapeutic Chemical classification system.
- 5.4.3.2 Adverse events will be coded using the Medical Dictionary for Regulatory Activities (MedDRA) Version 19.1 terminology or higher.

	DOCUMENT NUMBER: 029-BST-PLN-001	PAGE: 24 of 45
TITLE: Statistical Analysis Plan for study:  A Phase 2 Randomized, Double-Blind, Placebo-Controlled, Parallel-Cohort Study to Evaluate the Efficacy, Safety, Tolerability, and Pharmacokinetics of Once-Daily Application of Topical VDA-1102 Ointment for 28 Days in Subjects with Actinic Keratosis	EFFECTIVE DATE : 22/MAY/2017 REVISION NUMBER : 2.0	

#### 5.4.4 Handling of Missing Data

5.4.4.1 Assuming the scope of missing data of the primary efficacy endpoint will be significant, data imputation will be applied. Missing data at random imputation (MAR) will be performed for those subjects with missing efficacy data. Multiple imputation will be applied using SAS PROC MI to perform the imputations. Sensitivity analysis will be used for detecting differences between the analyses with and without data imputation.

#### 5.4.5 Protocol Violations and Deviations

5.4.5.1 Violation – Any enrolled subject who does not meet the study enrollment criteria (see Inclusion and Exclusion Criteria in Section 8 in the study protocol) will be considered a violation.

5.4.5.2 Deviation – Any activity that diverges from the procedures defined by this clinical protocol will be considered a deviation.

5.4.5.2.1 A major deviation is one that will definitely, probably or possibly significantly impact the subject safety or the quality of the trial data. Major deviation includes:

5.4.5.2.1.1 Subject was reduced to every other day dose by investigator at any point during the study

5.4.5.2.1.2 Subject who received study drug dosing on fewer than 20 days. The number of days of dosing will be based upon: (a) the “start dose date” and “stop dose date” days and (b) the compliance data reported in the EDC from the subject diaries and coordinator telephone calls. Subjects who received 1 or 2 doses of study drug on Day 1 Dosing will both be considered having been dosed once, not twice, for this calculation only.

5.4.5.2.2 A minor deviation is one that does not, or is unlikely to, significantly impact subject safety or the quality of the trial data.

5.4.5.3 All violations and deviations must be recorded in the study site’s electronic system and signed by the Investigator (or designee).

5.4.5.4 It is the Sponsor’s responsibility to determine whether the event will be considered a violation, major deviation, or minor deviation.

MediStat Statistics in Medicine	DOCUMENT NUMBER: 029-BST-PLN-001	PAGE: 25 of 45
TITLE: Statistical Analysis Plan for study:  A Phase 2 Randomized, Double-Blind, Placebo-Controlled, Parallel-Cohort Study to Evaluate the Efficacy, Safety, Tolerability, and Pharmacokinetics of Once-Daily Application of Topical VDA-1102 Ointment for 28 Days in Subjects with Actinic Keratosis	EFFECTIVE DATE : 22/MAY/2017 REVISION NUMBER : 2.0	

	DOCUMENT NUMBER: 029-BST-PLN-001	PAGE: 26 of 45
TITLE: Statistical Analysis Plan for study:  A Phase 2 Randomized, Double-Blind, Placebo-Controlled, Parallel-Cohort Study to Evaluate the Efficacy, Safety, Tolerability, and Pharmacokinetics of Once-Daily Application of Topical VDA-1102 Ointment for 28 Days in Subjects with Actinic Keratosis	EFFECTIVE DATE : 22/MAY/2017 REVISION NUMBER : 2.0	

## 5.5 Subject Population for Analyses

### 5.5.1 Intent-to-Treat Population

- 5.5.1.1 The ITT population will be defined as all subjects who are randomized and who receive at least one dose of study drug. This is an appropriate population for the primary analysis and for exploratory analyses because this is a blinded trial and the 1st dose will be applied in the clinic by the research clinic staff per protocol.
- 5.5.1.2 All safety analyses will be performed on the ITT population. Subjects will be analyzed according to the treatment actually received, not the treatment they were supposed to have received.

### 5.5.2 Modified ITT (mITT) Population

- 5.5.2.1 The mITT population includes all ITT patients who completed the study and have protocol deviations or protocol violations that are not expected to significantly impact efficacy (e.g. the total treatment area > or < 25 cm^2).
- 5.5.2.2 The mITT population will also be used for the primary efficacy endpoint analysis.
- 5.5.2.3 The mITT population will also be used for exploratory analyses. Analyses on Day 56 will include mITT subjects who completed Day 56 regardless of whether or not they also completed Day 84, and analysis on Day 84 will include mITT subjects who completed Day 84.

### 5.5.3 Per-Protocol Population

- 5.5.3.1 The PP population includes all ITT patients who have no violations or major protocol deviations.
- 5.5.3.2 The PP population will also be used for the primary efficacy endpoint analysis.
- 5.5.3.3 The PP population will also be used for exploratory analyses. Analyses on Day 56 will include PP subjects who completed Day 56 regardless of whether or not they also completed Day 84, and analysis on Day 84 will include PP subjects who completed Day 84.

 Statistics in Medicine	DOCUMENT NUMBER: 029-BST-PLN-001	PAGE: 27 of 45
TITLE: Statistical Analysis Plan for study: A Phase 2 Randomized, Double-Blind, Placebo-Controlled, Parallel-Cohort Study to Evaluate the Efficacy, Safety, Tolerability, and Pharmacokinetics of Once-Daily Application of Topical VDA-1102 Ointment for 28 Days in Subjects with Actinic Keratosis	EFFECTIVE DATE : 22/MAY/2017 REVISION NUMBER : 2.0	

#### 5.5.4 Pharmacokinetic Population

5.5.4.1 The subjects (maximum of 18) enrolled in the PK Study Sub-Cohort at approximately 3 sites will constitute the PK population.

MediStat Statistics in Medicine	DOCUMENT NUMBER: 029-BST-PLN-001	PAGE: 28 of 45
TITLE: Statistical Analysis Plan for study:  A Phase 2 Randomized, Double-Blind, Placebo-Controlled, Parallel-Cohort Study to Evaluate the Efficacy, Safety, Tolerability, and Pharmacokinetics of Once-Daily Application of Topical VDA-1102 Ointment for 28 Days in Subjects with Actinic Keratosis	EFFECTIVE DATE : 22/MAY/2017 REVISION NUMBER : 2.0	

## 5.6 Statistical Analysis

### 5.6.1 General

5.6.1.1 All measured variables and derived parameters will be listed individually and, if appropriate, tabulated by descriptive statistics. For categorical variables summary tables will be provided giving sample size, absolute and relative frequency and 95% CI (Confidence Interval) for proportions (if appropriate) by treatment group. For continuous variables summary tables will be provided giving sample size, arithmetic mean, standard deviation, coefficient of variation CV% (if appropriate), median, minimum and maximum and 95% CI (Confidence Interval) for means of variables (if appropriate) by treatment group. The data will be analyzed using the SAS ® version 9.3 or higher (SAS Institute, Cary North Carolina). Analyses presented in the clinical report but not mentioned in the SAP are unplanned or ad-hoc analyses.

5.6.1.2 Statistical methods presented in the SAP may be slightly different from those that are presented in the protocol. Differences are clearly stated in this SAP which supersedes the protocol only with regard to the way data will be handled and analysed.

### 5.6.2 Derived Data

#### 5.6.2.1 Definition of baseline

5.6.2.1.1 Baseline is defined as the last non-missing value prior to the patient start of treatment (i.e., Day1 Pre-dose, if available, otherwise Screening). All tabulations involving change from baseline data will only include patients with data at baseline and at follow-up.

#### 5.6.2.2 End of Study

5.6.2.2.1 The end-of-study visit is defined as Day 56 for protocol Version 1 and protocol amendment 1 and as Day 84 for protocol Amendment 2.

#### 5.6.2.3 Early Termination

MediStat Statistics in Medicine	DOCUMENT NUMBER: 029-BST-PLN-001	PAGE: 29 of 45
TITLE: Statistical Analysis Plan for study:  A Phase 2 Randomized, Double-Blind, Placebo-Controlled, Parallel-Cohort Study to Evaluate the Efficacy, Safety, Tolerability, and Pharmacokinetics of Once-Daily Application of Topical VDA-1102 Ointment for 28 Days in Subjects with Actinic Keratosis	EFFECTIVE DATE : 22/MAY/2017 REVISION NUMBER : 2.0	

5.6.2.3.1 If a subject who received at least 1 dose of the study drug wishes to withdraw from the trial, study staff should ask the subject to complete as many as possible of the planned evaluations scheduled through Day 84, as appropriate. If the subject declines, the subject should be asked to undergo the Day 28 safety and efficacy procedures.

5.6.2.4 Incomplete dates

5.6.2.4.1 All incomplete dates will be entered in the database as they were recorded in the CRF. Thereafter, for calculation purposes, the incomplete dates will be completed using pre-defined rules. If a day or month is recorded as UNK it will be replaced by the first day of the month or January respectively, provided this does not contradict any other dates recorded.

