### 12.3 Study Periods

The clinical trial will consist of the following periods:

- Screening: Days -21 through Day 1 Pre-dose
- Treatment: Day 1 Dosing through Day 28
- Observation: Day 29 through Day 84

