##### ✓ *Screening Visit (Day -21 to Day -1)*

The following procedures are to be performed during the Screening Visit:

- Site personnel confirm that the ICF: (a) is the most current ICF; (b) was signed and dated by the subject, (c) was witnessed; and (d) was copied with one copy given to the subject for their personal records
- Demographics recorded
- Medical history recorded
- Concomitant medications documented
- Adverse events that occur following ICF signing will be recorded
- Height and weight recorded

- Vital Signs: oral temperature, peripheral blood pressure, heart rate, and respiratory rate will be recorded
- Physical examination
- Clinical laboratory tests: Fasting status will be recorded
- Urine pregnancy test will be performed in all females and the results will be recorded
- 12-lead ECG tracing recorded as per the ERT manual. An original (duplicate) copy of the ECG is required for trial documentation. This ECG will also be transmitted to the central ECG laboratory.
- Scalp and face examination by PI (or designee) with selection of a Treatment Field that meets the criteria stated in Section 11.1. The Treatment Field Map and Template will be prepared as per the Investigator
- AK lesions count (11.1.5) and grading (11.1.1)
- Study Drug Measurement and Application review (see Section 13.6.3). Subject will be trained to measure (using placebo ointment on the Dosing Card) and to accurately apply the study drug, without actually applying placebo ointment to their Treatment Field
- Subject instructions review will be reviewed including appointment for the next visit
- Inclusion and exclusion (enrollment) criteria applied by Investigator and recorded
- Investigator may declare of subject's potential eligibility for PK Study Sub-Cohort

Subjects who are eligible for the **PK Study Sub-Cohort** will undergo the following additional safety assessments:

- ❖ Review additional Exclusion Criteria for PK subjects
- ❖ Toxicology and drug screen
- ❖ Alcohol level

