**✓ Day 1 Pre-Dose Visit**

Subjects who have completed all screening procedures and continue to meet the study enrollment criteria will return to the investigative site on Day 1 Pre-Dose. During this visit, the following procedures will be performed:

- Vital signs: oral temperature, peripheral blood pressure, heart rate, and respiratory rate will be recorded
- Adverse event(s): volunteered, elicited, and observed AEs will be recorded

- Concomitant medications documented
- Study Drug Measurement and Application review (see Section 13.6.3) should be one of the first procedures performed upon arrival at the site. The Treatment Field Map and Template will be prepared as per the Investigator instruction sheet.
- Subject will be trained to measure (using placebo ointment on the Dosing Card) and to accurately apply the study drug, without actually applying placebo ointment to their Treatment Field
- Physical examination
- Fitzpatrick skin typing (Section 9.3.2)
- Local Skin Reaction Score (baseline)
- AK Lesions in the Treatment Field: baseline count (11.1.5) and grading (11.1.1)
- Urine pregnancy test will be performed in all females and results recorded.
- 12-lead ECG tracing will be recorded as per the ERT manual. An original (duplicate) copy of the ECG is required for trial documentation. This ECG will also be transmitted to the central ECG laboratory
- Study Drug Application: Training and Testing (see Section 13.6.3) should be repeated after all the above activities have been completed. Subject will be trained to measure (using placebo ointment on the Dosing Card) and to accurately apply the study drug, without actually applying placebo ointment to their Treatment Field.
- Safety data from Screening, all available data from the Day 1 Pre-Dose Visit, as well as the Enrollment Criteria will be reviewed and approved by the Investigator (or designee)

Subjects who meet the study enrollment criteria will undergo the following procedures:

- Randomization of subjects
- Clinical laboratory tests: Fasting status will be recorded.
- Photographs of Treatment Field at designated sites
- Study drug weighed and recorded

Subjects enrolled in the **PK Study Sub-Cohort** will undergo the following additional procedure:

- ❖ Notify IWRS that the subject was enrolled in the PK Study Sub-Cohort to enable proper randomization and treatment assignment
- ❖ Blood sampling for (baseline) PK

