## 15. ADVERSE EVENTS

### 15.1 Adverse Event Definition

An AE is any untoward medical occurrence in a subject administered a pharmaceutical product, which does not necessarily have to have a causal relationship with the pharmaceutical product treatment. Any worsening of the subject's disease under study or other medical conditions will also be considered to be an AE, unless it is within the normal range of disease fluctuation for that subject.

**In this trial LSRs will be collected independently of AEs. Any LSR that occurs within the selected Treatment Field and extends to adjacent surrounding skin (defined as within a 2 cm border around the Treatment Area) will be considered LSRs and will not be recorded as AEs. LSRs that require medical intervention (prescription medication) or extend beyond the 2 cm surrounding skin should be documented as an AE.**

Clinically meaningful (for a given subject) changes in physical examination and test findings should also be recorded as AEs. The criteria for determining whether an abnormal objective test finding should be reported as an AE are as follows:

1. Test result is associated with accompanying symptoms, and/or
2. Test result requires additional diagnostic testing or medical/surgical intervention, and/or
3. Test result leads to a change in study dosing or discontinuation from the study, significant additional concomitant drug treatment, or other therapy, and/or
4. Test result leads to any of the outcomes included in the definition of a SAE.

Merely repeating an abnormal test, in the absence of any of the above conditions, does not meet Condition 2 above for reporting as an AE.

Any abnormal test result that is determined to be an error does not require reporting as an AE.

Treatment Emergent Adverse Events (TEAEs) are AEs that occur *de novo* or worsen following the initiation of study treatment.

Surgical procedures themselves are not AEs; they are therapeutic measures taken for the AE, and should be documented as such.

Planned hospital admissions documented in the subject's CRF prior to randomization and study-related procedures are also not AEs.

Overdoses of the study drug will not be reported as an AE. However, any AEs or SAEs, as defined in Section 15, associated with an overdose will be reported as such.

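### The SAP's single rule for incomplete dates can place an on-treatment adverse event before the first dose and so drop it from the treatment-emergent tables

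*SAP*

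**What the plan says.** SAP 5.6.2.4 keeps incomplete dates in the database as recorded and then says that "for calculation purposes, the incomplete dates will be completed using pre-defined rules". The rule is: "If a day or month is recorded as UNK it will be replaced by the first day of the month or January respectively". It carries one condition: "provided this does not contradict any other dates recorded". There is no separate rule for AE onset, AE stop or medication dates. The section does not say which dates can contradict, or what value is used when one does.

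Treatment-emergent status depends on timing. Protocol 15.1 states: "Treatment Emergent Adverse Events (TEAEs) are AEs that occur" for the first time or "worsen following the initiation of study treatment". AE collection starts earlier than that. At the Screening Visit, "Adverse events that occur following ICF signing will be recorded", and AEs are recorded again at the Day 1 Pre-Dose Visit: "Adverse event(s): volunteered, elicited, and observed AEs will be recorded". Protocol 12.3 sets the pre-dose period as "Screening: Days -21 through Day 1 Pre-dose".

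SAP 5.6.7.4 summarizes both AEs and TEAEs by treatment group. In SAP Appendix I, Tables 14.3.1-1 to 14.3.1-4 cover all AEs and Tables 14.3.1-5 to 14.3.1-8 cover TEAEs. Appendix II has a TEAE listing (16.2.7-1) and a listing for all other AEs (16.2.7-2).

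**The concern.** For an onset date, the rule picks the earliest day that the known parts allow. That is the choice least likely to leave the event classed as treatment-emergent. If the onset month is the month of first dose and dosing did not begin on the 1st, the completed date falls before dosing.

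The proviso does not clearly prevent this. Because AEs are collected from consent, a pre-dose onset is a legitimate AE date and does not conflict with the first-dose date. Where the 1st of the month falls before consent, the proviso can block the completed date, but the programmer then has no value to use.

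An onset error of this kind can only lower the TEAE count. Safety and tolerability is a secondary objective, arms have about 28 subjects, and the only table titled for serious events (14.3.1-8) is restricted to treatment-emergent ones. One or two misdated events could change a displayed incidence.

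**Working it through.** The plan states no figure for this, so there is none to reproduce. The check is a calendar calculation.

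**Inputs from the documents**
- Unknown day becomes the 1st; unknown month becomes January (SAP 5.6.2.4).
- Consent is up to 21 days before first dose (Protocol 12.3).
- Treatment runs over Days 1-28, and AEs are recorded to Day 84 (Protocol 12.3 and Table 5).

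**Assumptions**
- First-dose dates are spread evenly over the calendar.
- Consent is 1 to 21 days before dosing, each equally likely.
- True onset is uniform over a window of W days starting on Day 1.
- TEAE status is derived from the completed onset date.

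**Unknown day, proviso ignored.** Take a 30-day month with first dose on day D. The event moves if D > 1 and onset falls in the same month. The share moved is min(W, 31 − D)/W. For W = 28 this is 21/28 = 75% for D = 10, 11/28 = 39% for D = 20, and 0% for D = 1. Averaged over D = 1 to 30:
- W = 28: 434/(30 × 28) = 51.7%
- W = 84: 435/(30 × 84) = 17.3%
- W = 7: 182/(30 × 7) = 86.7%

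**Unknown day, a date before consent counts as a contradiction.** The 1st survives only if consent was on or before it, that is, at least D − 1 days before dosing. The probability is (23 − D)/21 for D = 2 to 22 and 0 after that. Summing min(W, 31 − D) × (23 − D) over D = 2 to 22:
- W = 28: 5138/(30 × 21 × 28) = 29.1%
- W = 84: 5159/(30 × 21 × 84) = 9.7%
- W = 7: 1617/(30 × 21 × 7) = 36.7%

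Enumerating every first-dose day of one real year, with true month lengths, gives nearly the same results:

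| Onset window | Proviso ignored | Date before consent blocked | Blocked, no value given |
|---|---|---|---|
| Days 1-7 | 87% | 36% | 51% |
| Days 1-28 | 52% | 29% | 23% |
| Days 1-84 | 18% | 10% | 8% |

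**Unknown month (completed to 1 January).** With the proviso ignored, 96% of Day 1-28 events move. With the consent check, an event moves only if first dose is on 2-22 January and consent was on or before 1 January. The sum of (23 − D)/21 over those days is 231/21 = 11, and 11/365 = 3%.

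**Undercount of Day 1-28 TEAEs.** This is f × p, where f is the share of events with an unknown onset day and p is the share moved. The documents do not give f; 1% to 10% is assumed.
- With the consent check (p = 0.291): 0.3% to 2.9%
- Proviso ignored (p = 0.523): 0.5% to 5.2%

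**The case against.** The strongest reply is that the proviso already does the work. AEs are elicited at the Day 1 Pre-Dose Visit. If an event is absent there and first reported on Day 7, a pre-dose onset can be said to conflict with the record, and on that reading nothing is misclassified. It is a sensible reading, but the SAP does not state it. The proviso speaks of contradicting other recorded dates, and a visit with no AE entered supplies no AE date.

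Several points on this side do stand:
- Exposure is limited. Visits fall on Days 7, 14, 28, 35, 56 and 84, there is weekly contact during treatment, and missing data are queried with the sites.
- The main local tolerability measure is untouched. Skin reactions within the field and its 2 cm border are scored separately and are generally not AEs.
- A misdated event remains in the all-AE tables and in a listing, and the rule is the same for every arm.
- Protocol 15.3 defers instructions on AE start and stop dates to a Safety Monitoring Plan that is not among the documents. It may reduce the number of partial dates.

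A reader might also infer that the rule shortens events when applied to stop dates, or shifts on-treatment medication into the pre-dose tables. The documents give little support for either as a material effect. No listed table title reports AE duration. Continuing routine medication must have been stable for at least 2 months before Screening, so many partial medication start dates would truly be pre-dose.

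**Conclusion.** The gap is real and small. Followed as written, SAP 5.6.2.4 can date an on-treatment AE before the first dose, and it leaves other events with no completed date at all. Only events with an unknown onset day in the calendar month of first dose are exposed to any extent; the unknown-month route is mostly closed once a date before consent counts as a contradiction.

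A reader might infer that the rule certainly undercounts TEAEs, or that about half of partially dated on-treatment events would be lost. The documents do not support either. The 52% figure ignores the proviso and uses the Day 1-28 window; 29% is the figure with a consent check, and over Days 1-84 the two become 18% and 10%. The number of partial AE dates is unknown and probably small.

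The percentages rest on uniform onset and uniform consent timing. The undercount range also rests on the assumed 1-10% of partial dates. The existence of the gap rests on none of these.

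**What to change.** Add an AE-onset rule to SAP 5.6.2.4:
1. If the known month and year (or the year alone) equal those of the first dose, complete the onset as the first-dose date, unless the stop date or other recorded data show that the AE began before dosing.
2. Otherwise use the first of the month or January, as now.
3. Class an AE as treatment-emergent unless the known date parts or the stop date show that it began before the first dose.
4. For the proviso, state which dates count as contradicting and what value is then used.

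This removes misclassification of on-treatment AEs from this source. The cost is one paragraph of SAP text. The downside is that TEAE counts may rise slightly, because a few truly pre-dose events may be counted as treatment-emergent.
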